8.3.5 Causality collection

The Investigator will assess causal relationship between study treatment and each AE, and answer 'yes' or 'no' to the question 'Do you consider that there is a reasonable possibility that the event may have been caused by the study treatment?'

For SAEs, causal relationship will also be assessed for other medication and study procedures. Note that for SAEs that could be associated with any study procedure the causal relationship is implied as 'yes'.

A guide to the interpretation of the causality question is found in [Appendix B](#) to the CSP.

8.3.6 Adverse events based on signs and symptoms

All AEs spontaneously reported by the patient or reported in response to the open question from the study site staff: '*Have you had any health problems since the previous visit/you were last asked?*' or revealed by observation will be collected and recorded in the eCRF. When collecting AEs, the recording of diagnoses is preferred (when possible) to recording a list of signs and symptoms. However, if a diagnosis is known and there are other signs or symptoms that are not generally part of the diagnosis, the diagnosis and each sign or symptom will be recorded separately.

8.3.7 Adverse events based on examinations and tests

The results from the CSP-mandated laboratory tests and vital signs will be summarized in the Clinical Study Report (CSR).

The Investigator should make an assessment of the available laboratory results with regard to clinically relevant abnormalities and should determine if any of the laboratory values are clinically significant. The laboratory results should be signed and dated and retained at study site as source data for laboratory variables.

Any protocol-mandated laboratory values or vital signs from the baseline visit that the Investigator assesses to be clinically significant, should be reported in the medical history. Deterioration as compared to baseline of any protocol-mandated laboratory values or vital signs that the Investigator assesses to be clinically significant should be reported as AEs. If deterioration of a laboratory value or vital sign meets the seriousness criteria, it should be reported as an SAE. If the reason for discontinuation of study treatment is due to deterioration of a laboratory value or vital sign compared to baseline (whether or not considered clinically significant), this should be reported as an AE. If a laboratory value or vital sign is outside the normal range, and the Investigator has assessed it as not clinically significant and study treatment has not been discontinued as a result of the laboratory value or vital sign, this does not need to be reported as an AE.

If deterioration in a laboratory value/vital sign is associated with clinical signs and symptoms, the sign or symptom will be reported as an AE and the associated laboratory result/vital sign will be considered as additional information. Wherever possible, the reporting Investigator uses the clinical, rather than the laboratory term (eg, anemia versus low Hb value). In the absence of clinical signs or symptoms, clinically relevant deteriorations in non-mandated parameters should be reported as AE(s).

Deterioration of a laboratory value, which is unequivocally due to disease progression, should not be reported as an AE/SAE.

Any new or aggravated clinically relevant abnormal medical finding as compared with the baseline assessment will be reported as an AE unless unequivocally related to the disease-under study (DUS), see Sections 8.3.9 and 8.3.10.

8.3.8 Hy's Law

Cases where a patient shows elevations in liver biochemistry may require further evaluation and occurrences of $AST \text{ or } ALT \geq 3x \text{ ULN}$ together with $TBL \geq 2x \text{ ULN}$ may need to be reported as SAEs. Please refer to [Appendix D](#) for further instruction on cases of increases in liver biochemistry and evaluation of Hy's Law (HL).

8.3.9 Disease-under study (DUS)

Symptoms of DUS are those which might be expected to occur as a direct result of CKD or procedures to diagnose or treat the CKD. Events which are unequivocally due to DUS should not be reported as an AE during the study unless they meet SAE criteria or lead to discontinuation of the study treatment.

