For cardiovascular (CV) safety, the dialysis-dependent (DD) patients including incident dialysis (ID) patients (a sub-group of DD patients who have been on dialysis for ≤ 4 months at the time of randomization) receiving roxadustat have a comparable risk of major adverse cardiovascular events (MACE, defined as stroke, myocardial infarction, all-cause death), MACE+ (events that comprised MACE plus hospitalized unstable angina and congestive heart failure), and all-cause mortality, compared with those who were treated with epoetin alfa. The CV safety of roxadustat has also been established in non-dialysis patients compared to placebo. The risk of MACE, MACE+ or all-cause mortality is similar between the treatment groups (roxadustat compared to placebo).

The overall safety profile of roxadustat was generally comparable to placebo for NDD CKD patients and to epoetin alfa for DD and ID CKD patients for most of the safety issues evaluated. A number of adverse drug reactions (ADRs) were identified, including vascular access thrombosis, deep vein thrombosis, and seizures. Serious infection was considered an important potential risk, but causality was not established. These risks are considered to be manageable with routine risk minimization activities.

The benefit-risk in this study is therefore deemed acceptable, when the study treatments are used in accordance with the rHuEPO and roxadustat China Package Inserts.

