5.1 Inclusion criteria

Patients are eligible to be included in the study only if all of the following inclusion criteria and none of the exclusion criteria apply:

Informed consent

- 1 Provision of signed and dated, written informed consent form (ICF) prior to any mandatory study specific procedures, sampling, and analyses.

The ICF process is described in Appendix A 3.

Age

- 2 Patient must be ≥ 18 years of age, at the time of signing the ICF.

Type of patient and disease characteristics

At Visit 1 prior to screening

Dialysis patients:

- 3 Patients receiving HD or PD for treatment of ESRD for at least 12 weeks. Patients treated with HD must have access consisting of an arteriovenous (AV) fistula, AV graft, or tunneled (permanent) catheter. Patients on PD must have a functioning PD catheter in place.
- 4 Hemodialysis patients should be on 3x/week dialysis with evidence of achievement of adequate dialysis as defined by $\text{stdKt/V} \geq 2.1$ in HD, and total (renal + PD) weekly $\text{Kt/V} \geq 1.7$ in PD documented twice during the 16 weeks preceding screening for the study.
- 5 Patients should be on a stable rHuEPO dose as defined by change in rHuEPO dose, not exceeding 20% within 4 weeks prior to screening.

Non-dialysis patients:

- 6 Patients with estimated glomerular filtration rate (eGFR) < 30 mL/minute/1.73 m², (calculated by central laboratory) corresponding to Stage 4 or Stage 5 CKD according to the Kidney Disease Outcomes Quality Initiative (KDOQI), and not receiving dialysis (Levey et al 2006).
- 7 Patients should either be on a stable dose of rHuEPO for 4 weeks before screening (defined as not exceeding 20% within 4 weeks prior to screening) or be rHuEPO-naïve (no ESA treatment for > 6 weeks before screening).

Dialysis and non-dialysis patients:

- 8 Patients agree not to take any new traditional Chinese medicine (TCM) and not to change, dose, schedule or brand of any TCM from beginning of the Screening Period through the end of the Follow-up Period.

At Visit 1 (screening)

- 9 Ferritin ≥ 50 ng/mL and transferrin saturation (TSAT) $\geq 15\%$ in non-dialysis patients (obtained from Visit 1, Screening Visit).
- 10 Ferritin ≥ 100 ng/mL and TSAT $\geq 20\%$ in dialysis patients (obtained from Visit 1, Screening Visit).

Weight

- 11 At Visit 1 (screening), dry body weight 45 to 100 kg (inclusive).

During the Screening Period

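### The disease-under-study rule in 8.3.9 makes no exception for the roxadustat reactions named in 2.3, so a non-serious vascular access thrombosis can go unrecorded, and possibly unequally by arm

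*Protocol*

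**What the plan says.** Protocol Section 8.3.9 defines symptoms of the disease under study as those "expected to occur as a direct result of CKD or procedures to diagnose or treat the CKD". It then sets the reporting rule: "Events which are unequivocally due to DUS should not be reported as an AE during the study unless they meet SAE criteria". A second exception keeps events that make the patient stop treatment. Section 8.3.7 applies the same test to examinations and tests: a new or aggravated clinically relevant finding "will be reported as an AE unless unequivocally related to the disease-under" study.

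Section 2.3 states what is known about the drug: "A number of adverse drug reactions (ADRs) were identified, including vascular access thrombosis, deep vein thrombosis, and seizures". Section 5.1, criterion 3, fixes who has a vascular access: "Patients treated with HD must have access consisting of an arteriovenous (AV) fistula, AV graft, or tunneled (permanent) catheter".

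Section 3 makes the incidence of AEs part of the safety endpoint, and Section 9.4.4 summarises AEs by arm, descriptively. Section 8.3.2 has all AEs collected from consent through follow-up. It adds a 24-hour report for roxadustat adverse drug reactions, which it defines as AEs that the investigator thinks roxadustat may have caused. Appendix B 1 defines an AE without regard to causal relation to the drug.

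**The concern.** The exclusion in 8.3.9 turns on cause: the investigator decides what an event is due to, and that decision settles whether it is recorded as an AE at all. This is a common rule for symptoms of the underlying disease. Here, however, the disease under study is extended to the procedures that treat it, and one known reaction to the test drug is an event that arises at the site of such a procedure. Neither 8.3.9 nor 8.3.7 says what to do when the same event fits both descriptions.

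The judgment is made at the site in an open-label trial. Section 4.2 defends the open label on the ground that the endpoints are measured levels. That reasoning does not reach an AE count that has already been filtered by attribution. An event that is not recorded cannot be restored in the analysis, and the trial has no data monitoring committee (Section 9.5.1). What is at stake is the between-arm description of a reaction that the protocol itself lists as known.

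**Working it through.** No arithmetic applies, because the documents give no rate of access thrombosis in either arm. The check is whether the sections, read together, allow the event to be left out, and whether another section brings it back.

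**Step 1: can the event fall under the definition?** Section 8.3.9 includes results of procedures that treat CKD. It does not name dialysis, but dialysis is the plain example, and 5.1 gives every HD patient a fistula, graft or tunneled catheter. A clotted access can be read as a result of such a procedure.

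**Step 2: can it fall under the exclusion?** Only if it is judged unequivocally due to the disease under study, is not serious, and does not lead to stopping study treatment. All three conditions must hold.

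**Step 3: is there an exception for known drug reactions?** Neither 8.3.9 nor 8.3.7 contains one. Section 2.3 lists the reactions but gives no recording rule.

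**Step 4: does another section close the gap?**
- Section 8.3.2, general rule: it collects all AEs, but an event excluded under 8.3.9 is not reported as an AE.
- Section 8.3.2, 24-hour rule: it applies to events already classed as AEs, and only to roxadustat.
- Appendix B 1: its definition disregards cause, whereas 8.3.9 removes events because of their cause. The two are not reconciled.
- Appendix B 8: it asks the investigator to weigh the known drug profile, but as part of assessing the causality of an AE.
- Appendix B 2 and B 6: an event may be serious without hospitalization if it could jeopardize the patient or need intervention to prevent a listed outcome. Some access thromboses would qualify and be reported. This narrows the gap but does not close it.

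**Step 5: is the effect the same in both arms?** For an event that is non-serious and does not stop treatment:

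| How the investigator reads the unequivocal test | Roxadustat arm | rHuEPO arm |
|---|---|---|
| Strictly: a recognised drug cause means the event is not unequivocally due to dialysis | Recorded | May go unrecorded; 2.3 names no rHuEPO cause |
| Loosely: a clotted access is attributed to dialysis | May go unrecorded | May go unrecorded |

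The strict reading can make recording unequal by arm. The loose reading can lose the known reaction in both arms. The protocol does not say which applies. The rHuEPO column rests on the protocol alone. The rHuEPO package insert is not at hand, and if it names the same reaction, the strict reading would tend to have the event recorded in both arms.

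**The case against.** The strongest reply is that the word unequivocally does the work. An investigator who has read 2.3 knows that roxadustat is a recognised cause of access thrombosis and can hardly call such an event unequivocally due to dialysis in a roxadustat patient. On that view 2.3 and 8.3.9 can both be followed without contradiction. Serious events and those that stop treatment are reported in any case, and Appendix B 2 and B 6 make the serious class wider than hospitalization. What remains is a narrow set of events, observed over about six weeks (2 weeks of treatment plus 4 of follow-up), in a safety objective analysed descriptively.

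Much of this stands. A reader might infer that 8.3.9 makes every event arising from dialysis non-reportable, or that it removes all non-serious access thrombosis. The text does not support either: the exclusion is confined to unequivocal cases, has two exceptions, and leaves the rest to judgment.

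The reply does not remove the point. The protocol nowhere says that a known reaction can never be unequivocally due to the disease under study. If that is the intended reading, it protects recording in the roxadustat arm and leaves the rHuEPO arm under a different test, which is itself a problem for a comparison between arms.

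**Conclusion.** The point holds in a limited form. Section 8.3.9 lets a non-serious vascular access thrombosis that does not stop treatment be left out of the AE endpoint if the investigator judges it unequivocally due to CKD or its treatment. That judgment is unblinded, and no section exempts the reactions named in 2.3. The same event may be recorded in one arm and not in the other.

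The size and direction of the effect cannot be derived from the documents. It bears only on the descriptive safety comparison. The primary endpoint, an area under the serum iron curve, is untouched. A reader might infer that the trial will miss a known harm, or that the bias favours one drug. Neither is shown: recording depends on how each investigator applies the test, and Step 5 allows under-recording in the rHuEPO arm alone or in both arms.

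The conclusion rests on two readings: that dialysis and its access count as procedures that treat CKD, and that an event excluded under 8.3.9 does not reach the reporting rules for AEs. Both are natural, but the protocol states neither outright.

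**What to change.** Reconcile 8.3.9 and 8.3.7 with 2.3, 8.3.2 and Appendix B 1. Add one sentence to 8.3.9, cross-referenced in 8.3.7: vascular access thrombosis, and for consistency the other reactions named in 2.3 (deep vein thrombosis and seizures), are recorded as AEs in both arms, whether or not the investigator attributes them to CKD or to dialysis. Causality is then assessed on the recorded event, as 8.3.5 already provides. How these events are tabulated can be left to the SAP.

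This is a data-recording rule only and changes no dose, treatment or clinical care. It needs no new visit or procedure. The cost is the added wording, a reminder to sites, and a few more non-serious AE entries.

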8.3.10 Disease progression

Disease progression can be considered as a worsening of a patient's condition attributable to the disease for which the study treatment is being studied. It may be an increase in the severity of the DUS and/or increases in the symptoms of the disease. Worsening of anemia should not be considered an AE unless the worsening of anemia is associated with a cause other than the patient's CKD. Events, which are unequivocally due to disease progression, should not be reported as an AE during the study.

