8.4 Safety reporting and medical management

8.4.1 Reporting of serious adverse events

All SAEs have to be reported, whether or not considered causally related to the study treatment, or to the study procedure(s). All SAEs will be recorded in the eCRF.

If any SAE occurs in the course of the study, then Investigators or other site personnel inform the appropriate AstraZeneca representatives within 1-day ie, immediately but **no later than 24 hours** of when he or she becomes aware of it.

The designated AstraZeneca representative works with the Investigator to ensure that all the necessary information is provided to the FibroGen Drug Safety **within 1 calendar day** of initial receipt for all SAEs. FibroGen Drug Safety will be responsible for processing all SAEs.

For fatal or life-threatening AEs where important or relevant information is missing, active follow-up is undertaken immediately. Investigators or other site personnel inform AstraZeneca representatives of any follow-up information on a previously reported SAE within 1 calendar day ie, immediately but **no later than 24 hours** of when he or she becomes aware of it.

The Investigator is obliged to report SAE to the appropriate local regulatory authorities, Ethics Committees and AstraZeneca representative within 24 hours of SAE awareness.

Safety information (SAEs, serious adverse drug reactions [SADRs], adverse drug reactions [ADRs] and suspected unexpected serious adverse reactions [SUSARS]) are to be reported by

Sponsor or Sponsor Representative to the appropriate local regulatory authorities within legally binding timelines.

Once the Investigators or other site personnel indicate an AE is serious in the electronic data capture (EDC) system, an automated email alert is sent to the designated AstraZeneca representative.

If the EDC system is not available, then the Investigator or other study site staff reports a SAE to the appropriate AstraZeneca representative by telephone.

The AstraZeneca representative will advise the Investigator/study site staff how to proceed.

For further guidance on the definition of a SAE, see [Appendix B](#) of the CSP.

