An adverse drug reaction (ADR) is the development of an undesirable medical condition or the deterioration of a pre-existing medical condition following or during exposure to a medicinal product, suspected to be causally related to the product.

B 4 Life-threatening

‘Life-threatening’ means that the patient was at immediate risk of death from the AE as it occurred, or it is suspected that use or continued use of the product would result in the patient’s death. ‘Life-threatening’ does not mean that had an AE occurred in a more severe form it might have caused death (eg, hepatitis that resolved without hepatic failure).

B 5 Hospitalization

Outpatient treatment in an emergency room is not in itself a serious AE, although the reasons for it may be (eg, bronchospasm, laryngeal edema). Hospital admissions and/or surgical operations planned before or during a study are not considered AEs if the illness or disease existed before the patient was enrolled in the study, provided that it did not deteriorate in an unexpected way during the study.

B 6 Important medical event or medical treatment

Medical and scientific judgement should be exercised in deciding whether a case is serious in situations where important medical events may not be immediately life-threatening or result in death, hospitalization, disability or incapacity but may jeopardize the patient or may require medical treatment to prevent one or more outcomes listed in the definition of serious. These should usually be considered as serious.

Simply stopping the suspect drug does not mean that it is an important medical event; medical judgement must be used.

- Angioedema not severe enough to require intubation but requiring intravenous hydrocortisone treatment
- Hepatotoxicity caused by paracetamol (acetaminophen) overdose requiring treatment with N-acetylcysteine
- Intensive treatment in an emergency room or at home for allergic bronchospasm
- Blood dyscrasias (eg, neutropenia or anemia requiring blood transfusion, etc.) or convulsions that do not result in hospitalization
- Development of drug dependency or drug abuse

B 7 Intensity rating scale:

The Investigator should use the National Cancer Institute (NCI) Common Terminology Criteria for Adverse Events (CTCAE) version ≥ 5.0 . For terms not specified as part of NCI-CTCAE, the following guidelines should be used to determine grade:

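### Sections 8.3.7, 8.3.9 and 8.3.10 give conflicting reporting rules for serious events due to worsening of the disease under study, so such events can be captured inconsistently or missed

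*Protocol*

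**What the plan says.** Three neighbouring protocol sections say when worsening of the disease is kept out of AE reporting.

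- **Section 8.3.9 (disease under study).** Events unequivocally due to the disease under study "should not be reported as an AE during the study unless they meet SAE criteria or lead to discontinuation of the study treatment".
- **Section 8.3.10 (disease progression).** Progression is a worsening of the condition being treated: "It may be an increase in the severity of the DUS and/or increases in the symptoms of the disease". The section then states: "Worsening of anemia should not be considered an AE unless the worsening of anemia is associated with a cause other than" the patient's CKD. It closes with: "Events, which are unequivocally due to disease progression, should not be reported as an AE during the study". No exception follows either sentence.
- **Section 8.3.7 (examinations and tests).** A laboratory or vital-sign deterioration that meets seriousness criteria is to be reported as an SAE, and one that is the reason for stopping study treatment is to be reported as an AE. Later in the same section: "Deterioration of a laboratory value, which is unequivocally due to disease progression, should not be reported as an AE/SAE".

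Two general provisions also bear on the point. Section 8.4.1 states: "All SAEs have to be reported, whether or not considered causally related to the study treatment", and extends this to study procedures. Appendix B 2 defines an SAE as an AE that fulfils at least one seriousness criterion, and Appendix B 6 includes anemia needing transfusion among its examples of important medical events.

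**The concern.** A progression event under Section 8.3.10 is by definition a worsening of the disease that Section 8.3.9 covers, so one event can fall under both. The two sections give opposite instructions when that event is serious or leads to stopping of study treatment. Section 8.3.7 contains the same conflict within itself for laboratory values.

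AE incidence is part of the safety endpoint (Section 3, Table 2), and AEs and SAEs are summarized by treatment group (Section 9.4.4). SAE reports are also to be evaluated individually (Section 8.2), which cannot happen for an event that is never entered. The trial is open-label and has no data monitoring committee (Section 9.5.1), so site reporting is the main route by which a serious event becomes visible.

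**Working it through.** No arithmetic applies, because the protocol gives no rate for such events. The check sets the rules side by side for four events that a site could meet, each judged unequivocally due to CKD or its progression.

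| Event | Reportable under | Not reportable under |
|---|---|---|
| Hospital admission for worsening CKD | 8.3.9 (hospitalization is a seriousness criterion in Appendix B 2) | 8.3.10, closing sentence |
| CKD-related anemia needing transfusion, without admission | 8.3.9, if judged an important medical event as in the Appendix B 6 example | 8.3.10, anemia sentence |
| Laboratory deterioration that meets seriousness criteria | 8.3.7, seriousness sentence; 8.3.9 | 8.3.7, progression sentence |
| Laboratory deterioration that is the reason for stopping study treatment | 8.3.7, discontinuation sentence; 8.3.9 | 8.3.7, progression sentence |

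Every row has an entry in both columns.

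**Does Section 8.4.1 settle it?** It requires every SAE to be reported whatever the cause. Three points stop it from clearly doing so:

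1. Under Appendix B 2 an SAE must first be an AE. The anemia sentence of Section 8.3.10 says that CKD-related worsening is not to be considered one, so a site applying it never reaches Section 8.4.1.
2. The progression sentence of Section 8.3.7 names the SAE expressly. It cannot be read as covering only non-serious events.
3. The automated alert in Section 8.4.1 is sent once a site marks an AE as serious in the data capture system. If no AE is entered, there is no alert.

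**Is precedence stated anywhere?** No. Section 8.3.7 sends the reader to Sections 8.3.9 and 8.3.10 together without ranking them. Appendix B 8 gives a causality rule for deterioration of the disease under study through lack of effect. That rule presupposes that such deterioration is sometimes recorded, but it does not say when.

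**Does the anemia sentence matter in this population?** It lacks the qualifier that the cause be unequivocal, which the other exclusions carry. Exclusion criterion 4 removes patients with other known causes of anemia, so CKD is the natural default attribution when anemia worsens.

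**The case against.** The strongest reply is that the sections can be read together. Progression is a form of disease-under-study event, so the exception in Section 8.3.9 reaches it, and Section 8.4.1 then requires the report. Appendix B 1 supports this: it counts deterioration of a pre-existing condition as an AE, so the closing sentence of Section 8.3.10 restricts reporting without redefining the event. This softens the conflict for that sentence. It does not help with the anemia sentence, which says the event is not an AE at all, or with Section 8.3.7, which removes the SAE in terms.

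Several further points stand and limit the concern:

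- Much of the information is captured elsewhere. Hemoglobin is measured centrally on Days 1, 8 and 15 in all patients, hematology is summarized by visit and arm, rescue therapy is recorded in the eCRF (Section 6.5.3), and vital status is sought at the end of the study (Section 7.3). Laboratory summaries do not, however, replace an SAE record of an admission or a transfusion.
- Appendix B 6 is a generic list of examples for judging seriousness. It does not itself decide when CKD anemia is an AE.
- Exposure is short: two weeks of treatment and four of follow-up. Patients likely to start dialysis within 3 months are excluded (exclusion criterion 18).
- Safety is analyzed descriptively, and no efficacy conclusion is affected.

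A reader might also infer that anemia caused by a study treatment would go unreported. The text does not support that: such anemia has a cause other than CKD, so Section 8.3.10 keeps it as an AE.

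**Conclusion.** The inconsistency is in the current text and should be corrected. A site that follows Section 8.3.10, or the progression sentence of Section 8.3.7, would omit serious events that a site following Section 8.3.9 or 8.4.1 would report. What is established is that capture can be inconsistent and events can be missed.

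A reader might go further and infer that the safety endpoint will be undercounted, or that the arms will be affected differently. The documents show neither. Sites following Section 8.3.9 or 8.4.1 would report these events. Open-label attribution makes a difference between arms possible, but nothing in the protocol demonstrates one.

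The size cannot be derived. With 20 to 60 patients randomized 1:1, one patient is 1/30 = 3.3% to 1/10 = 10% of an arm. That is only the weight of one patient and says nothing about how many events would be missed. Overall AE incidence would move by that amount only if the patient had no other AE. The number of events may be small.

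Leaving out non-serious progression events is a legitimate choice and is not criticized. The defect is the missing exception for events that are serious or that lead to stopping of study treatment.

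**What to change.** Reconcile the three sections using the exception that the protocol already has in Section 8.3.9 (the event meets SAE criteria, or leads to stopping of study treatment):

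- **Section 8.3.10:** add the exception to the closing sentence, and state that the anemia sentence is subject to it.
- **Section 8.3.7:** add the exception to the progression sentence and strike the SAE term, so that the sentence limits only AE reporting.

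This brings both sections into line with Sections 8.3.9 and 8.4.1 and with Appendix B. It changes no dose, schedule or treatment rule. The cost is a few sentences of protocol text and possibly a few more SAE forms.
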